6.6 Interim analyses and stopping rules

After the first cohort of baseline data collection we will analyse the completeness, reliability and validity of outcomes questionnaires (including the outcomes measures described above). We will do this by exploring:

- Percentages of scale item completeness.
- Outcome measure means, standard deviations and skew.
- Cronbach Alpha testing for scale reliability.

This analysis will not include a comparison between control group and treatment group data nor analysis of impact. We will review and discuss these findings with Future Men and YEF to provide reassurance that data collection is proceeding well. If there are concerns, we will suggest and discuss solutions with YEF and Future Men.

We will continue to monitor data quality looking at scale completeness, means, standard deviations and skew throughout the trial for internal purposes to ensure that data collection proceeds smoothly. If on review we have concerns, we will raise this with YEF and Future Men as appropriate.

The trial will stop if the BDP is unable to recruit a sufficient number of participants. Recruitment rates will be regularly monitored against modelled target rates, and reviewed as part of project group meetings. Any decisions about stopping will be made in discussion with YEF and Future Men colleagues.

The Future Men project team will also be responsible for safeguarding of participants. They will report any serious adverse events overall and by trial arm. The trial will stop if Future Men, YEF and Cordis Bright decide that the BDP is unsafe for participants.

6.7 Longitudinal follow-up analyses

As discussed in section 6.2, boys in both groups will complete outcomes measures at both 12 and 24 weeks post-randomisation. We will conduct longitudinal analysis of covariance to assess the extent to which the impact of the BDP on school engagement has been sustained. This will be conducted in line with the longitudinal ANCOVA approach recommended in Twisk et al. (2018), and will take the following form:

$$\begin{split} Y_{i} &= \beta_{0} + \beta_{1}Baseline_{i} + \beta_{2}Group_{i} + \delta School_{k} + \beta_{4}Time_{it} + \beta_{5}Group_{i} * Time_{it} \\ &+ \varepsilon_{i} \in N(0, \sigma^{2}) \end{split}$$

Where:

- β_2 reflects the treatment effect at 12 weeks post randomisation.
- *Time_{it}* is a dummy variable for 24 weeks post randomisation.
- $\beta_2 + \beta_5$ is the treatment effect at 24 weeks post randomisation.

We will report both point estimates and confidence intervals for impact estimates at both 12 and 24 weeks post randomisation. Differences between the two and their implications will be discussed in the final report.

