5.2 Whole cohort

We have determined the overall sample size for the trial a priori, in line with YEF guidance. These calculations suggest that a final sample size of 422 (211 per group) would ensure that the efficacy study is sufficiently powered to detect a statistically significant result if it exists (power = 0.80, two tailed, p < 0.05). Please note that our planned sample size for the trial is 480 boys, in line with Future Men's capacity to deliver the intervention. This provides buffer for attrition throughout the trial of 12% (58 boys). However, the final sample for the trial will not be finalised until randomisation is complete in April 2025. We will update Table 2 with

the final figures once they are known. Our approach to estimating the sample size for this efficacy study is conservative and has been influenced by the following:

- **YEF guidance.** YEF guidance suggests that efficacy study RCTs should have a Minimum Detectable Effect Size (MDES) of 0.20.
- Available data on the School Connectedness Questionnaire. The primary outcome measure for the study is school engagement, as measured by Marsh and Randolph's (2020) School Connectedness Questionnaire. In their validation study, Marsh and Randolph (2020) reported mean average scores, standard deviations and skew for each of the three SCQ sub-scales across two samples one for a sample of young people in general education, and one for a sample for young people experiencing emotional and behavioural disorders. Total scores and the associated standard deviation were not reported in Marsh and Randolph's (2020) paper, and data on pretest and post-test correlations has also not been published. As such, we have drawn from available data on similar measures (see below).
- Available data on similar measures. As described above, pre-test post-test correlations for the SCQ have not been published. Therefore, we draw from available data on the Student Engagement in Schools Questionnaire (Lam et al., 2014, p.38). For this scale, six month test-retest results were found to be 0.73 for the full-scale. In line with our conservative approach, we have therefore suggested a pre-test/post-test correlation of 0.7.

[figure not shown]

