Table 2 at the start of this section presents power calculations which have been conducted in line with the above approach. These power calculations suggest that a sample size of 211 in each group (i.e. 422 in total) will be sufficiently powered to detect a statistically significant result if it exists (power = 0.80, two tailed, MDES = 0.195).³

[figure not shown]
Future Men's delivery capacity enables them to deliver the BDP intervention to a maximum of 240 boys over the duration of the study. With a control group allocated as close as is feasible to a one-to-one ratio, this means a total sample size of 480 boys is achievable under existing plans. Based on the power calculation above, this means even with attrition or non-completion of questionnaires for 38 boys (12%, which is slightly above YEF's desired target of no more than 10% attrition) the sample should be able to detect statistically significant differences if they exist.

³ These power calculations have been conducted using PowerUp. Available here: https://www.causalevaluation.org/power-analysis.html [Last accessed 17/06/2024].

Update: March 2025

Baseline data collection was completed in February 2025, with 483 baseline surveys collected (i.e, 3 more than our target of 480). Of these, 243 boys are in the BDP group, and 240 are in the signposting group, which is in line with our 1:1 allocation ratio target. The CONSORT diagram below presents this in more detail.

Maintaining the above assumptions of a 12% attrition rate, this suggests that the trial will have a final sample of 425 questionnaires at T2. Rounded down to 424 (i.e. 212 in each group), power calculations suggest that this will result in a final MDES of 0.195.

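### As printed, the section 6.7 longitudinal model omits within-boy correlation, so it overstates the standard error of the change in effect from 12 to 24 weeks (by about 30% if those scores correlate 0.7)

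*SAP*

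**What the plan says.** SAP section 6.7 states its purpose: "We will conduct longitudinal analysis of covariance to assess the extent to which the impact of the BDP on school engagement has been sustained". It also says that "boys in both groups will complete outcomes measures at both 12 and 24 weeks post-randomisation", so a boy with complete follow-up contributes two outcome scores.

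The equation it prints has the baseline score, allocation group, school dummies, a dummy for 24 weeks and the product of group and time. It defines β2 as the effect at 12 weeks and β2 + β5 as the effect at 24 weeks, so β5 is the change in effect. There is one normal error with variance σ². The time dummy carries a time subscript; the outcome and the error do not. Neither this section nor any other gives a random effect for boy, a residual covariance matrix or boy-clustered standard errors. The section says that the model follows a longitudinal ANCOVA approach from a cited methods paper.

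The plan promises an estimate and a confidence interval for the effect at each of the two times, and then: "Differences between the two and their implications will be discussed in the final report". It names no interval or test for β5 and no rule for calling the impact sustained. Section 6.2 makes 12 weeks the primary time point, with its own single-time ANCOVA.

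**The concern.** Two scores from one boy remain correlated after adjustment for baseline. A model with independent errors treats 424 boys with two scores each as 848 unrelated observations. For most coefficients the usual worry is an interval that is too narrow. Here it runs the other way for β5: that coefficient compares each boy's later score with his earlier one, so a positive correlation should shrink its variance, and the printed model does not allow that.

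β5 is the parameter that answers the question section 6.7 asks. An interval that is too wide makes a real fading of the effect harder to detect.

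A second, smaller worry is dropout. With independent errors the model keeps the 12-week score of a boy who is missing at 24 weeks, but borrows nothing from it for the 24-week effect. Section 6.9 confines its missing-data analyses to the primary outcome analysis, so no other protection is stated for the 24-week estimate.

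**Working it through.** **Inputs from the SAP (section 5.2).** The design values are "power = 0.80, two tailed, MDES = 0.195" with 211 boys per group, and a pre/post correlation r = 0.7. The expected analysed sample is 424 (212 per group) after 12% attrition. A six-month test-retest value of 0.73 is cited for a similar scale.

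**Assumptions.** The correlation r12 between the 12- and 24-week scores is not given; I take 0.7 with a range of 0.5 to 0.8. The baseline correlation of 0.7 is applied at both follow-up times, and all 424 boys are taken to have both scores. Units are SDs of the outcome.

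**Step 1: the plan's own figure.** MDES = (1.960 + 0.842) × √[(1 − 0.7²) × 4/422] = 2.802 × √(0.51 × 4/422) = 0.1948, or 0.1952 with t quantiles. The stated 0.195 is reproduced, so the residual variance of 0.51 is the right starting point.

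**Step 2: standard error of β5.**
- Printed model, independent errors: √(2 × 0.51 × 4/424) = 0.0981; 95% half-width 1.96 × 0.0981 = 0.192.
- Residual correlation given baseline: ρ = (r12 − r²)/(1 − r²). At r12 = 0.7 this is 0.21/0.51 = 0.412.
- With that correlation: 0.0981 × √(1 − 0.412) = 0.0752; half-width 0.147.
- Ratio: 1/√(1 − ρ) = √[0.51/(1 − r12)] = √(0.51/0.30) = 1.30.

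| r12 | ρ | Printed SE ÷ correct SE |
|---|---|---|
| 0.5 | 0.020 | 1.01 |
| 0.6 | 0.216 | 1.13 |
| 0.65 | 0.314 | 1.21 |
| 0.7 | 0.412 | 1.30 |
| 0.73 | 0.471 | 1.37 |
| 0.8 | 0.608 | 1.60 |

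With complete data the ratio does not depend on the sample size.

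**Step 3: simulation of the printed model** (ordinary least squares on stacked data, 424 boys, six schools, 3,000 runs). The mean model SE against the empirical SD of β5 was:
- 0.0980 against 0.0853 at r12 = 0.6 (ratio 1.15);
- 0.0979 against 0.0735 at 0.7 (1.33; coverage of the nominal 95% interval 99.3%);
- 0.0978 against 0.0609 at 0.8 (1.61);
- 0.1041 against 0.0760 when r12 = 0.7 but the baseline-to-24-week correlation falls to 0.6 (1.37).

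**Step 4: consequence at r12 = 0.7.** A nominal 5% test of β5 has a true size of 2 × [1 − Φ(1.96 × 1.304)] = 1.1%. Power to detect complete fading of a 0.195 SD effect is 51% with the printed model and 74% with the correct standard error. For fading by half it is 10% and 25%.

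**Step 5: the intervals the plan does promise.** In the same simulations the SE ratio was 1.00 to 1.06 for β2 and 0.94 to 1.00 for β2 + β5. The extremes come from the case with unequal baseline correlations, where one pooled σ² fits neither time exactly.

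**Step 6: dropout.** In illustrative simulations with about 10% to 14% missing at 24 weeks, depending on the 12-week score, bias in the 24-week effect was negligible (at most about 0.004 SD) when dropout worked alike in both arms. It was roughly 0.01 to 0.04 SD when the mechanism differed between arms.

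**The case against.** The strongest reply is that the notation is merely loose. The section cites a longitudinal ANCOVA approach, section 6.2 describes the same source as also advocating repeated-measures analysis, and nowhere does the SAP say that the two scores are independent or that ordinary least squares will be used. This stands in part: a correlated-error model may well be intended, and the cited paper is not at hand to settle it. But the plan says the analysis takes the printed form, and section 6.1 leaves the SPSS syntax until all data are in. The equation is therefore the only pre-specification, and it shows no within-boy covariance.

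It is also fair that the harm falls on an interval the SAP does not promise, that the promised intervals are close to right, and that the error is conservative for β5. With complete data, adding a random intercept would leave the point estimates unchanged. All of this stands and limits the weight of the point.

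Three stronger readings are tempting and are not supported:
- **That 30% is a minimum.** It rests on r12 = 0.7, which the SAP does not state. The cited 0.73 makes such a value plausible, but at 0.6 the excess is 13% and at 0.5 about 1%.
- **That the plan is tilted towards declaring the impact sustained.** This needs someone to read a β5 interval that includes zero as proof of lasting impact. The SAP states no such rule; it promises only discussion.
- **That 24-week dropout related to the 12-week score will bias the result.** Step 6 shows that this matters only if the dropout mechanism differs between arms.

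**Conclusion.** The point holds in limited form. Followed as printed, the section 6.7 model gives the wrong standard error for the one coefficient that measures whether the effect lasted. The overstatement is about 30% on the assumption that the 12- and 24-week scores correlate 0.7, with a range from about 1% to 60% for correlations of 0.5 to 0.8, taking both baseline correlations as 0.7. The primary result is not at risk, and neither time-specific interval is materially wrong. What is at stake is precision on the sustained-impact question, from data the trial collects anyway. It should be corrected, but it does not threaten the trial's main conclusion.

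**What to change.** In section 6.7:

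1. Index the outcome and the error by time (Y_it, ε_it).
2. Add a random intercept for boy, or an unstructured 2×2 residual covariance for the two times, fitted by REML on all available 12- and 24-week scores. Keep baseline, school, group, time and group × time. The unstructured form also allows the residual variance to differ between times.
3. Commit to reporting β5 with its confidence interval beside the two time-specific effects.
4. State how β5 will be read, and that a non-significant β5 will not be taken as proof that the impact was sustained.

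The cost is a few lines of SAP text. SPSS MIXED fits either structure, and no further data are needed. Section 6.1 already foresees a finalised analysis plan, in which the change can be made.

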6.8 Imbalance at baseline

If randomisation has been successful, both treatment and business-as-usual groups should be equivalent at baseline. As such, any imbalance will have occurred by chance. To check for and monitor imbalance at baseline, we will produce a table of descriptive characteristics for all young people at baseline. We will also produce an equivalent table for those included in the final analysis sample, to check whether any attrition experienced throughout the trial may have introduced an imbalance. These descriptive characteristics will include:

- Age.
- Sex.
- Ethnicity.
- Free school meal eligibility.
- English as an additional language.
- SEND status.
- Baseline SCQ scores.

Baseline SDQ scores.

Data on pupil characteristics is provided by school partners through the initial referral form. We will present a cross-tabulation of counts and percentages for each category above against allocation group. For continuous variables, we will present the means and standard deviation. This analysis will be used to inform our understanding of the extent to which our initial sample was balanced across the two groups, and whether any attrition experienced throughout the trial has introduced an imbalance. We will discuss any differences and their implications in the final report.

6.9 Missing data

Throughout the trial, the evaluation team will work closely with the Future Men team to support the collection of high quality and complete data for all boys. However, missing data may occur due to either item non-completion or sample attrition (i.e. boys who do not complete either T2 or T3 questionnaires). We will assess both the extent of missingness and patterns of missingness in the data. In line with YEF guidance we will report on both: (1) the proportion of missing data in the trial, and (2) the extent and pattern of missingness in the data. This will involve analysis of whether data is missing completely at random (MCAR), missing at random (MAR), or missing not at random (MNAR). MCAR and MAR mean that complete cases are unlikely to be biased subsequent to adjustment but may be underpowered, while MNAR suggests that structural bias has been introduced to the sample.

We will attempt to establish the missing mechanism (i.e. which variables in the data are predictive of non-response) through logistic regression models. This will model the presence of missing outcomes data with additional information that may be predictive of missingness. We will conduct this analysis in line with the flow chart in Figure 1 in the YEF analysis guidance.⁶ This outlines the following approach:

- If the prevalence of missing data is less than 5%, no further action is required as complete case analysis is unlikely to be biased.
- If outcomes data is MAR conditional on co-variates, we will include these co-variates in our primary analysis model and discuss the implications in full.
- If a covariate is MAR conditional on other covariates, we will conduct multiple imputation (MI). Treatment effects from the MI analysis will be reported in addition to

⁶ Available here, page 15: https://res.cloudinary.com/yef/images/v1623145483/cdn/6.-YEF-Analysis-Guidance.pdf [Last accessed 12/12/2023]

estimates from the model outlined in section 6.2. Any differences between the two and their implications will be discussed in full.

• If missing data cannot be fully explained by the other variables in the dataset, data is likely to be MNAR. In this scenario we will conduct a sensitivity analysis alongside the primary impact analyses.

We will only conduct the above analyses for the primary outcome analysis, as all secondary outcomes analysis, subgroup analysis and further analysis is tentative and exploratory in nature.

Unfortunately, there is no universally agreed approach to analysis in the event of item noncompletion. In the event that a high proportion of cases would be excluded due to low rates of item non-completion (for example, if most boys miss a small number of items), our approach to missing data will balance considerations around data integrity with maximising statistical power. In this scenario, we would consider using statistical techniques to impute missing items. We will finalise and agree our approach to this for the final draft of the Statistical Analysis Plan in line with YEF guidance, i.e. once baseline data collection is complete and we have a greater understanding of the structure of the data.

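### Section 6.9 makes its only test of departure from MAR depend on a regression that cannot tell MAR from MNAR, with no criterion for the trigger and no named method

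*SAP*

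**What the plan says.** Section 6.9 sets out how the mechanism is to be found: "We will attempt to establish the missing mechanism (i.e. which variables in the data are predictive of non-response) through logistic regression models". Four branches follow, for the primary outcome only.

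- **Under 5% missing:** complete cases, with nothing further: "If the prevalence of missing data is less than 5%, no further action is required as complete case analysis is unlikely to be biased".
- **Outcome MAR given covariates:** "If outcomes data is MAR conditional on co-variates, we will include these co-variates in our primary analysis model".
- **Covariate MAR given other covariates:** multiple imputation, reported in addition to the section 6.2 model.
- **Missingness not fully explained:** "If missing data cannot be fully explained by the other variables in the dataset, data is likely to be MNAR". The action is "In this scenario we will conduct a sensitivity analysis alongside the primary impact analyses".

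The fourth branch holds the only analysis in the SAP that could address departure from MAR. Its method is not named, and no rule says when missingness counts as fully explained.

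Section 5.2 plans for losses well above the 5% cut-off. The March 2025 update applies "Maintaining the above assumptions of a 12% attrition rate" to 483 boys and expects 425 questionnaires at T2.

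**The concern.** Data are MNAR when missingness still depends on the unseen score after conditioning on what was observed. A regression of non-response on observed variables contains no information about that remaining dependence. Finding predictors does not rule out MNAR, and finding none does not show it. The rule nevertheless uses this regression to decide whether departure from MAR is examined at all.

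The error that matters is the false reassurance. If the analysts judge that covariates explain the missingness, they adjust for them or impute. Both remedies assume MAR, and the plan then asks for nothing more.

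The setting makes this more than a formal point. The primary outcome is self-reported school engagement in boys referred because they are at risk of disengagement or exclusion, so non-response related to the unseen score is plausible. If that relation or the attrition rate differs between arms, the primary estimate is biased, and the plan does not guarantee an analysis that would show by how much.

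**Working it through.** **Inputs from the SAP.** 483 boys with baseline surveys (243 BDP, 240 signposting); 12% attrition; MDES 0.195; power 0.80; two-sided alpha 0.05; pre/post correlation 0.7 (all section 5). ANCOVA on baseline, group and school (section 6.2).

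**The plan's own figures.** 483 × 0.88 = 425.04, which the SAP rounds down to 424. MDES = (1.960 + 0.842) × √[(1 − 0.7²)/(0.25 × N)]. This gives 0.1948 at N = 422 and 0.1943 at N = 424 with normal quantiles (0.1952 and 0.1948 with t quantiles). The stated 0.195 reproduces. At 12%, about 58 of 483 boys are lost; the 5% branch ends at about 24 (0.05 × 483 = 24.15). The later branches will therefore probably apply.

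**Shift 1: equal attrition, different contrast.** Let p be the fraction missing in each arm, D_obs the baseline-adjusted contrast in observed boys and D_mis that in missing boys. The full-sample effect is (1 − p)D_obs + pD_mis, and an analysis assuming MAR estimates D_obs. The bias is p(D_obs − D_mis). The departures below are assumptions, since the SAP gives none.

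| Departure (SD) | Shift at p = 0.12 | Share of 0.195 |
|---|---|---|
| 0.1 | 0.012 | 6% |
| 0.2 | 0.024 | 12% |
| 0.3 | 0.036 | 18% |
| 0.5 | 0.060 | 31% |

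The upper end is a large departure. With a correlation of 0.7 the residual SD is √0.51 ≈ 0.71, so 0.5 SD is about 0.7 residual SDs.

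**Shift 2: different attrition, same departure.** If dropouts in both arms score δ below their MAR prediction, the bias is δ(p_T − p_C). Assume 8% in one arm and 16% in the other, which averages 12%. The size is then 0.08δ: 0.008 SD at δ = 0.1 (0.008/0.195 = 4%) and 0.04 SD at δ = 0.5 (0.04/0.195 = 21%). The sign depends on which arm loses more boys.

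**Can the regression discriminate?** I simulated 2,000 trials per scenario with 243 and 240 boys, no true effect, correlation 0.7 and about 12% missing. Each was analysed by baseline-adjusted ANCOVA without school terms, and missingness was regressed on baseline and arm. The dropout strengths are assumptions: where used, −0.6 log-odds per SD of baseline and −1 log-odds per outcome SD of the unseen residual.

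| Dropout depends on | Baseline significant | Bias (SD) | Type I error |
|---|---|---|---|
| Baseline only (MAR) | 98% | 0.002 | 5% |
| Baseline, plus unseen residual in BDP arm | 98% | 0.059 | 13% |
| Baseline, plus unseen residual equally in both arms | 97% | 0.000 | 5% |
| Unseen residual in BDP arm only | 4% | 0.062 | 13% |
| Nothing (MCAR) | 5% | −0.001 | 6% |

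In the first two rows the regression looks the same, but only the second is biased. In the last two rows baseline again predicts nothing beyond chance, and only one is biased. The inability to discriminate follows from the definitions; the simulation shows what it can cost.

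**The case against.** **The trigger, read literally, is wide.** A reader might infer that any covariate that predicts non-response switches the sensitivity analysis off. The text does not say that. Its condition is failure to explain the missingness fully; partial prediction does not meet that standard, and the branches are not stated to be exclusive. On a strict reading the analysis would nearly always run. This stands, and it limits the point to an undefined trigger. The same words also let the analysts declare the data MAR and stop, and even when the analysis runs its method is open.

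**One misclassification is harmless.** Calling MCAR-like missingness MNAR only adds a cautious analysis beside the primary result. Agreed; the damage lies in the other direction.

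**Losing low-scoring boys is not enough for bias.** Also agreed. With equal outcome dependence in both arms the simulated bias was 0.000. The documents contain no evidence that dropout will differ by arm.

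**Other checks exist.** Section 6.8 promises a balance table for the final analysis sample, and section 6.9 reports the pattern of missingness. Both could reveal differential attrition. Neither reaches the unseen outcome, because both use observed variables.

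**The rule follows funder guidance, and the plan is a draft.** The cited flow chart cannot be inspected here and may give more detail, but it would not validate the inference that the SAP states. Section 6.1 promises finalisation after baseline. Version 1.1 postdates the end of baseline collection and lists only a section 5 change. The deferral at the end of section 6.9 concerns item non-completion, not attrition.

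**Conclusion.** The point holds. The rule infers the mechanism from data that cannot identify it, and it makes the only test of departure from MAR conditional on that inference, with neither a criterion nor a method. The primary result could therefore be reported at the planned 12% attrition without any such test.

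The possible size is modest to material: 0.012 to 0.060 SD with equal 12% attrition, or 0.008 to 0.04 SD with 8% against 16%, compared with an MDES of 0.195. These ranges rest on assumed departures of 0.1 to 0.5 SD and, in the second case, on assumed attrition rates. Both need a difference between arms, in outcome dependence or in attrition.

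A reader might go further and infer that the primary result will be biased, or that attrition goes wholly unexamined. The documents support neither. Bias is conditional on that difference between arms, and the SAP does commit to describing attrition and balance.

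**What to change.** In section 6.9, delete the sentence that infers MNAR from unexplained missingness. Keep the logistic model only to describe predictors of non-response and to choose auxiliary variables.

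Prespecify a delta-adjusted (pattern-mixture) tipping-point analysis of the 12-week primary SCQ outcome, with delta varied separately by arm. Run it whatever the missingness regression shows, at least whenever primary-outcome missingness is 5% or more, and report the delta at which the conclusion changes. State the range of delta before follow-up data are examined.

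The analysis should use the same score as the primary model. Section 6.2 names the sum of the three subscales as the primary outcome but defines the model's outcome as the school engagement subscale, so that must be settled first.

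The cost is a change of SAP wording and one additional sensitivity analysis. No new data are needed.

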4.2 Research questions

The key research question of the efficacy study is:

'Does a targeted, social-emotional learning programme for boys at risk of disengagement and exclusion improve school engagement in comparison to business as usual?'

Additional research questions are:

- 1. **Delivery**: Can the BDP work under ideal circumstances?
- 2. **Impact**: a) What is the impact of the BDP? b) Do different sub-groups of young people have different outcomes, e.g. those from minoritized/marginalised groups?
- 3. **Unintended consequences**: Does the BDP have any unintentional consequences? If so, what are these? Do different groups of young people experience these differently?
- 4. **latrogenic effects**: Are there any serious negative effects attributed to the BDP on any outcomes?
- 5. Mechanisms: Which factors contribute most to the observed outcomes?

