6.5 Further analyses

We will conduct the following exploratory further analysis:

• The impact of positive relationships. We will evaluate the extent to which positive relationships between the young person and project co-ordinator (treatment group) or significant adult (control group) influenced the primary outcome over and above the impact of the BDP through the SSRS. We are proposing conducting this analysis because the theory of change suggests that the key mechanism of change for the BDP is that it has its effect through an increase in positive relationships with a trusted adult. This will take a mediation analysis approach, i.e. we will estimate the direct and indirect effects, following the approach outlined in Gunzler et al. (2013).

About the Social Support and Rejection Scale

The SSRS has 4 dimensions: Feels valued, trust, mentoring, and negativity. Each item is scored from 1 (never) to 5 (always). Each subscale score is the average of items that make up the subscale. Higher scores on the negativity scale reflect higher levels of stress and negativity within the relationship. For the overall scoring of the scale a high score represents a positive relationship.

• Improvements to school attendance and reductions to exclusion as measured by school administrative data. If we are able to access school administrative data which is of sufficient high quality, consistency and comparability across schools, we will explore whether there is a difference in attendance and exclusions between those in

the BDP group and those in the business-as-usual group. This will follow the same model as set out for the primary and secondary outcomes analysis.

• **Dosage and fidelity.** Any analysis relating to dosage and fidelity will be exploratory in nature. If power calculations suggest that the analysis will be sufficiently powered, we will explore the association between the level of dosage and the impact on the SCQ. This data will be captured by monitoring data on number of sessions received collected by the Future Men delivery team. This analysis will be conducted using a general linear model assuming normality, or a generalized linear model. It will answer questions such as: does attending 8 or more BDP sessions result in a similar impact as attending all 12 sessions?

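### Section 6.9 limits the missing-data analyses to the primary outcome, so the SDQ effects that bear on the harm question rest on complete cases alone

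*SAP*

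**What the plan says.** SAP section 4.2 lists as research question 4: "Are there any serious negative effects attributed to the BDP on any outcomes". Sections 4.3 and 6.3 make the SDQ emotional symptoms, externalising and peer-problem scores secondary outcomes, analysed with the ANCOVA model of section 6.2.

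Section 6.9 describes logistic models of missingness, covariate adjustment and multiple imputation. For data judged missing not at random (MNAR) it says: "In this scenario we will conduct a sensitivity analysis alongside the primary impact analyses". Its limit for accepting complete cases is: "If the prevalence of missing data is less than 5%, no further action is required". It then closes the list with: "We will only conduct the above analyses for the primary outcome analysis, as all secondary outcomes analysis, subgroup analysis and further analysis is tentative". The paragraph that follows concerns unanswered items, not boys who miss a whole survey.

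On expected loss, section 5.2 says: "Maintaining the above assumptions of a 12% attrition rate, this suggests that the trial will have a final sample of 425 questionnaires at T2".

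Three other provisions bear on the point:
- Section 6.8 tabulates baseline characteristics by arm, including baseline SDQ, again for the final analysis sample.
- Section 6.6 has serious adverse events reported by arm.
- Section 6.5 examines attendance and exclusions conditionally: "If we are able to access school administrative data which is of sufficient high quality, consistency and comparability across schools".

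**The concern.** The harm question covers every outcome, and the three SDQ scores are the self-report measures most likely to show a boy getting worse. Section 6.9 removes them from all missing-data work because they are exploratory. That label can excuse lighter treatment of a benefit claim. It fits a harm question less well, because there the error to fear is false reassurance.

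The plan's own limit points the same way. Complete cases need no further work below 5% missing, yet 12% is expected. The SDQ would be past the limit and barred from the steps that follow it.

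The trial recruits boys at risk of disengagement and exclusion. It is reasonable to suppose, though the SAP does not say so, that boys who deteriorate are likelier to miss a survey. If that happened more in one arm, the complete-case SDQ contrast would be biased. A finding of no worsening would then describe only the boys who stayed.

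**Working it through.** **Inputs from the SAP.** Allocation (section 5.2): "243 boys are in the BDP group, and 240 are in the signposting group". Expected loss 12%, expected T2 sample 425, rounded down to 424. Pre/post correlation r = 0.7, chosen for the school connectedness measure. Design settings: "power = 0.80, two tailed, p < 0.05", with a minimum detectable effect of 0.195 SD.

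**Assumed.** r = 0.7 for the SDQ too, with 0.5 as an alternative; the loss mechanism; the size of any shift. The SAP gives none of these for the SDQ.

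**1. The plan's own figures reproduce.** Minimum detectable effect = M × √[(1 − r²)/(0.25 N)], where M is the sum of the t quantiles for 0.975 and 0.80. With r² = 0.49 this gives 0.195 for N = 422 and 0.195 for N = 424, as in Table 2.

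**2. Expected loss.** 483 × 0.12 = 58 boys: 243 × 0.12 = 29.2 in the BDP arm and 240 × 0.12 = 28.8 in control. 12% is 2.4 times the 5% limit. (Section 5.2 also calls 38 boys 12%; 480 − 422 = 58, and 58/480 = 12.1%, so 58 is used here.)

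**3. Bias from a shift in one arm.** Suppose a fraction m of BDP boys is missing and they are d SD worse than observed BDP boys with the same baseline, while missing controls do not differ from observed controls. The complete-case effect is then too favourable by m × d.
- d = 0.5: 0.12 × 0.5 = 0.06 SD
- d = 1.0: 0.12 × 1.0 = 0.12 SD
- Hiding a worsening of 0.195 SD completely: d = 0.195/0.12 ≈ 1.6 SD

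**4. Precision for comparison.** 95% half-width = 1.96 × √[4(1 − r²)/N].
- r = 0.7: 1.96 × √(4 × 0.51/424) = 0.136 SD
- r = 0.5: 1.96 × √(4 × 0.75/424) = 0.165 SD

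**5. Simulation.** 3,000 trials per scenario, 243 against 240 boys, true worsening of 0.195 SD in the BDP arm, complete-case ANCOVA on baseline (school term omitted). Detected means the estimate exceeds 1.96 standard errors in the harmful direction.

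| Loss mechanism | r = 0.7: estimate, detected | r = 0.5: estimate, detected |
|---|---|---|
| Random, 12% per arm | 0.195, 80% | 0.197, 65% |
| Odds of loss double per SD worse, both arms, 12% each | 0.197, 81% | 0.194, 65% |
| Same, but 16% BDP and 8% control lost | 0.165, 68% | 0.147, 44% |
| Odds double, BDP only (control random), 12% each | 0.150, 58% | 0.131, 35% |
| Odds triple, BDP only, 12% each | 0.128, 46% | 0.097, 22% |
| Worst 12% of BDP boys lost, control random | 0.071, 21% | 0.021, 5% |

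The second row matters as much as the others: the same mechanism at the same rate in both arms leaves the effect essentially unbiased.

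**The case against.** Restricting missing-data modelling to the primary outcome is an explicit, reasoned choice. The SAP never says that research question 4 will be answered by non-significant SDQ results, and it calls the secondary analyses tentative.

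A reader might infer that nothing planned could reveal the problem. The SAP does not support that.
- All measures come from the boys by online survey at the same time points. The missingness models and loss figures for the primary outcome will therefore largely describe SDQ loss as well.
- The section 6.8 table compares baseline SDQ by arm among those analysed. In the most extreme scenario above (r = 0.7) it would show a gap of about 0.16 SD.
- Serious adverse events are reported by arm.
- ANCOVA already allows for loss that depends on the scale's own baseline and on school.

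A reader might also infer that harm will be hidden. That needs loss which depends on the unobserved outcome and differs by arm. Controls come from the same at-risk population, and no document shows a difference. The illustration sets the control shift to zero. Its upper end, 1.0 SD at the same baseline, is 1.0/√0.51 ≈ 1.4 residual SDs, which is large for the average missing boy.

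These objections limit the point but leave its core. A loss pattern described for the primary outcome does not change an SDQ estimate. A baseline table cannot show worsening after baseline and triggers no further analysis. Adverse event reports do not measure change on the scales. Exclusion data are conditional.

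**Conclusion.** The point holds in a limited form. By a stated rule, the SDQ effects relevant to research question 4 would be complete-case estimates at an expected 12% loss, past the plan's own 5% limit, with no adjustment for predictors of missingness beyond baseline score and school and no MNAR sensitivity analysis.

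Partial masking of a worsening is possible; near-complete masking appears only under extreme assumptions. The illustrative bias of 0.06 to 0.12 SD is 44% to 88% of the 0.136 SD half-width (0.06/0.136 and 0.12/0.136). It rests on one-sided loss and on a correlation borrowed from another measure; at r = 0.5 the half-width is 0.165 SD. It is a scenario, not a forecast.

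The primary analysis is unaffected. What is insecure is a conclusion that the programme did not worsen the SDQ scores.

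**What to change.** In section 6.9, remove the restriction for the SDQ emotional symptoms, externalising and peer-problem scores when they are used to answer research question 4. For each score:
- report loss by arm at 12 and 24 weeks;
- include in the SDQ model the covariates found to predict missingness;
- run an MNAR sensitivity analysis, for example shifting the missing BDP boys in the harmful direction over a stated range and giving the shift at which the conclusion on harm changes.

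Report reasons for loss only where they are already recorded. A new reason field could not be completed for follow-ups already past: section 5.3 shows 116 boys onboarded by 4 January 2024.

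Section 6.1 already says the analysis plan will be revisited after baseline, so this fits a dated revision made before SDQ outcomes are compared by arm. The results can keep their exploratory label. The cost is a few extra model runs, with no new participants or data collection.
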